#### 4. Adverse events

All adverse events occurring at any time during the 12-month follow-up period will be reported, with distinctions made between ocular and systemic (patient level) events.

New variable	Rules	
Maximum intensity of SAE	Maximum of intensity variable on initial SAE form and all follow-up SAE forms	

#### 5. Proportion of patients with macular atrophy of the RPE

Macula atrophy of the RPE is defined as the presence of hypoautofluorescence in the study eye at 12 months and will be determined by AF.

New variable	Rules
Macular atrophy of the RPE (study eye)	YES: if at 12 month visit 'Is there homogenous hypo AF (representing atrophy) involving the fovea?' (SE_AF_HomogenousHypoAF) in study eye = YES NO: if at 12 month visit 'Is there homogenous hypo AF (representing atrophy) involving the fovea?' in study eye = NO MISSING: otherwise

#### 6. Area change in macular RPE hypoautofluorescence

Macular RPE hypoautofluorescence will be measured in the study eye by AF. Measurements at baseline and 12 months will be used to derive this outcome. Area change will be described; area of macular RPE at 12 months will be analysed, adjusting for baseline.

New variable	Rules	
Area of macular RPE (study eye)	Total area of hypo AF (atrophy) (SE_AF_HypoAFTotalArea)	
Area change in macular RPE	= (area of macular RPE at 12 months – area of macular RPE at baseline)	

#### 7. Choroidal thickness

Choroidal thickness will be measured by enhanced depth imaging OCT at 12 months. Measurements will be made sub-foveally. Choroidal thickness is recorded directly as a continuous variable (variable name: SE\_OCT\_MaxChoroidalThickness) and so no derivation is required.

#### 8. Proportion of patients with reduced choroidal permeability

Reduced choroidal permeability will be assessed by ICG at 12 months. Reduced choroidal permeability is recorded directly as yes or no (variable name: SE\_ICG\_ReducedChoroidalPermeability) and so no derivation is required.

#### 9. Time to resolution of SRF

Resolution of SRF will be assessed in the study eye at 4 weeks, 3, 6, 9 and 12 months.

New variable	Rules
SRF resolved (study eye)	YES: if 'Are there any areas of hyporeflectivity
	separating the neurosensory retina and the
	RPE/Bruch's Complex on any scan?'
	(SE_OCT_HyporeflectivityOnAnyScan) = NO
	NO: if 'Are there any areas of hyporeflectivity
	separating the neurosensory retina and the
	RPE/Bruch's Complex on any scan?' = YES
	MISSING: otherwise
Time to resolution of SRF (study eye)	= (Date of SRF resolution – date of randomisation)

#### 10. Classification of study eyes as complete, partial or no resolution of SRF

Classification of study eyes will be completed at each time point of the study. Partial resolution of SRF is defined as a decrease of >25% of CMT from baseline due to resolution of SRF. A non-responder is defined as having an increase in SRF or decrease in SRF  $\leq 25\%$  from baseline.

New variable	Rules
Central macular thickness (study eye)	Central subfield retinal thickness (SE_OCT_CentralSubfieldRetinalThickness)
Resolution of SRF (study eye)	COMPLETE RESOLUTION: if SRF has completely resolved
	PARTIAL RESOLUTION: if CMT has decreased by >25% from baseline
	NON-RESPONDER: if SRF increased or decreased by ≤25% from baseline
	MISSING: if CMT missing

#### 11. Patient-reported visual function

Patient-reported visual function will be assessed using the visual function questionnaire VFQ-25 which will be completed at baseline and 12 months.

Data from the VFQ-25 questionnaires will be used to derive 12 sub-scale scores and an overall composite score, with a higher score indicating a better level of functioning.

The National Eye Institute 25-Item Visual Function Questionnaire (VFQ-25) Version 2000 manual will be used to derive these scores .

#### To derive the sub-scores:

• Re-code original responses using the following scoring rules (**Table 1**) so all items are on a scale of 0 to 100.

Item number	Original response	Re-coded response
1, 3, 4, 15c 	1	100
	2	75
	3	50
	4	25
	5	0
2	1	100
	2	80
	3	60
	4	40
	5	20
	6	0
5, 6, 7, 8, 9, 10, 11, 12, 13, 14,	1	100
16, 16a	2	75
	3	50
	4	25
	5	0
	6	*

#### Table 1 Scoring key: recoding of items

17, 18, 19, 20, 21, 22, 23, 24, 25	1	0
	2	25
	3	50
	4	75
	5	100

 Item 15c has four-response levels but is expanded to five-levels using item 15b. Note: - If 15b = 1, then 15c should be recoded to 0

- If 15b = 2, then 15c should be recoded to missing - If 15b = 3, then 15c should be recoded to missing

\* Response choice 6 indicates that the person does not perform the activity because of non-visual related problems. If this choice is selected, the item is coded as missing.

To calculate the sub-scale scores, average the items within each sub-scale (Table 2). Items that are missing are not taken into account when calculating the scale scores. Sub-scales with at least one item answered can be used to generate a sub-scale score.

Scale		Number of items	Items to be averaged
General health		1	1
General vision		1	2
Ocular pain		2	4, 19
Near activities		3	5, 6, 7
Distance activitie	es	3	8, 9, 14
Vision specific:	Social functioning	2	11, 13
	Mental health	4	3, 21, 22, 25
	Role difficulties	2	17, 18
Dependency		3	20, 23, 24
Driving		3	15c, 16, 16a
Colour vision		1	12
Peripheral visior	ı	1	10

Table 2	Averaging	of	items to	o calculate	sub-scales
	/ to aging	•		/ ouroundto	000 000100

#### To derive an overall composite score:

To calculate an overall composite score, average the vision-targeted sub-scale scores (excluding the general health scale).

#### 12. Classification of all study eyes by each FFA phenotype

All study eyes will be classified by each FFA phenotype, e.g. smoke stack, ink-blot or chronic epitheliopathy at baseline and 12 months. FFA phenotype is recorded directly as smoke stack, ink-blot or chronic epitheliopathy for all participants (variable name: SE\_FA\_IfLeakageVisible) and so no derivation is required.

#### 13. Classification of all study eyes as early, late, or non-responder

All study eyes will be classified as early, late or non-responder. An early responder is defined as complete or partial resolution of sub-foveal SRF by 3 months. A late responder is defined as complete or partial resolution of sub-foveal SRF after 6 months. Resolution of sub-foveal SRF will be measured at baseline, 4 weeks, 3, 6, 9 and 12 months.

#### 14. Incidence of CSCR in the fellow eye

Incidence of CSCR in the fellow eye will be diagnosed by OCT, FFA, ICGA or AF at baseline, 4 weeks, 3, 6, 9 and 12 months. The proportion of patients with any CSCR in the fellow eye will be described and the proportion with new CSCR in the fellow eye will be compared between groups.

New variable	Rules
CSCR in fellow eye at baseline	YES: if right eye considered for eligibility = YES AND left eye considered for eligibility = YES
	NO: if either right eye considered for eligibility = NO or left eye considered for eligibility = NO
	MISSING: otherwise
Any CSCR (fellow eye)	YES: if either CSCR in fellow eye at baseline = YES OR CSCR in fellow eye = YES at any post-randomisation study visit NO: if CSCR in fellow eye at baseline = NO AND new CSCR in the fellow eye = NO at all post-randomisation study visite
	MISSING: otherwise
New CSCR (fellow eye)	YES: if CSCR in fellow eye at baseline = NO AND new CSCR in fellow eye = YES at any post-randomisation study visit NO: if either new CSCR in fellow eye = NO at all post- randomisation study visits OR CSCR in fellow eye at baseline =
	YES
	MISSING: otherwise

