#### 3.1 Flow of participants

Participant flow will be described via a flowchart (see **Figure F1**). Follow-up will last 12 months with follow-up visits planned at 1 week, 4 weeks, 3 months, 6 months, 9 months and 12 months post-randomisation.

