Protocol deviation 4 – visit attended but outside of study window	YES: if any visit attended falls outside the visit window NO: if all attended visits are within the visit windows MISSING: otherwise Visit windows: 1 week and restarting one week (+/- 1 day) 4 weeks and restarting four weeks (+/- 5 days) All other follow-up visits (+/- 10 days) Note: all visit windows are calculated from the date of randomisation, except re-starting visits which are calculated
Protocol deviation 5 – patient potassium exceeded 5.0mmol/L but patient was informed to continue treatment	YES: if patients potassium level was > 5.0mmol/L at any visit AND patient informed to continue treatment = YES NO: if patients potassium level was > 5.0mmol/L at any visit AND patient informed to continue treatment = NO OR patient potassium level ≤ 5.0mmol/L at all visits MISSING: otherwise
Protocol deviation 6 – incorrect dosage regimen followed	YES: if for any attended visit where the patient remained on the study treatment, the incorrect dose was prescribed. NO: if for all attended visits where the patient remained on the study treatment, the correct dose was prescribed. Correct dosage regimen: patient prescribed 25mg/day of treatment at baseline visit which is increased to 50mg/day after 1 week if the patients potassium level ≤ 5.0mmol/L. Patient continues on 50mg/day until there is evidence of complete resolution of SRF. If a patient restarts treatment during the study, the same dose escalation procedure will be followed i.e. patients will restart on 25mg/day increased to 50mg/day after 1 week.
Protocol deviation 7 – patient prescribed more bottles than required at study visit	
 
YES: if either:
 
Patient prescribed more than one bottle at baseline visit, 1 week visit or restarting visit
 
Patient prescribed more than two bottles at 4 week visit or restarting week 4 visit
 
Patient prescribed more than three bottles at 3 month, 6 month or 9 month visit
 
NO: if patient prescribed correct number of bottles at all study visits where treatment is continuing
 

Protocol deviation 8 – patients disease resolved but informed to continue treatment	YES: if at any study visit CSCR resolved = YES AND informed to continue treatment = YES NO: if either: • if CSCR resolved = NO at all attended study visits • if CSCR resolved = YES at any study visit AND informed to continue treatment = NO MISSING: otherwise

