- Time to event outcomes will be summarised by the median and IQR in each treatment group, estimated from Kaplan Meier curves. Outcomes will be compared using proportional hazards parametric survival models for interval-censored data. If the assumption of proportional hazards does not hold, other methods will be considered as appropriate. The choice of model used will depend on the outcome event and model assumptions. Treatment comparisons will be presented as hazard ratios (HRs) and 95% CI if a proportional hazards model is used, time ratios (TRs) and 95% CI if an accelerated failure time model is used, or odds ratios (OR) and 95% CI if a discrete time proportional odds model is used. Times will be censored using censoring variables defined below:

Outcome	Censor variable
Time to resolution of SRF	Date of last visit, if SRF did not resolve
Time to disease recurrence	Date of last visit, if SRF did not recur
Time to response (complete or partial)	Date of last visit, if disease did not resolve completely or partially
Time to incidence of CSCR in fellow eye	Date of last visit, if CSCR not present in fellow eye at any point by the end of follow-up

- Continuous longitudinal outcomes will be summarised as means and SDs (or medians and IQRs if distributions are skewed) at each time point. Outcomes will be compared using linear mixed effects methodology where the outcome of interest is collected at baseline, 4 weeks, 3, 6, 9 and 12 months, with the treatment group and study design variables fitted as per section 5.2.1, and patient terms fitted as random effects. Separate parameter estimates will be incorporated into models for 1) the mean baseline response across both treatment groups and 2) at each post-intervention time point for each treatment (i.e. saturated model with time fitted as a categorical variable). If the time x treatment interaction (postintervention) is not statistically significant at the 5% level an overall treatment effect will be reported. If the interaction is statistically significant the changes in treatment effect with time will be described. Different variance/covariance structures will be explored, and the structure that provides the best fit in terms of information criteria such as AIC, BIC and likelihood ratio tests will be used. Treatment comparisons will be presented as adjusted differences in means with 95% CI.

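### Read literally, the fellow-eye CSCR coding turns event-free patients with incomplete follow-up into MISSING but keeps patients with an event and the same gap as YES, so the descriptive proportions in Table T17 are distorted

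*SAP*

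**What the plan says.** SAP section 4.2, item 14, derives two post-baseline variables.

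- **New CSCR** is YES if the fellow eye was free at baseline and "new CSCR in fellow eye = YES at any post-randomisation study visit". It is NO "if either new CSCR in fellow eye = NO at all post- randomisation study visits", or if the fellow eye had CSCR at baseline. Otherwise it is MISSING.
- **Any CSCR** is YES from baseline disease or from one positive later visit. It is NO "if CSCR in fellow eye at baseline = NO AND new CSCR in the fellow eye = NO at all post-randomisation study" visits. Otherwise it is MISSING.

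The same item schedules fellow-eye assessment at baseline, 4 weeks and 3, 6, 9 and 12 months. It says that any CSCR will be described and that "the proportion with new CSCR in the fellow eye will be compared between groups".

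Section 3.1 has "follow-up visits planned at 1 week, 4 weeks, 3 months, 6 months, 9 months and 12 months post-randomisation", which is six visits, one more than the five with a fellow-eye assessment.

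Section 5.3.2 lists fellow-eye incidence as a time-to-event outcome, analysed with survival models for interval-censored data. Patients without the event are censored at "Date of last visit, if CSCR not present in fellow eye at any point by the end of follow-up". Table T17 gives an HR/TR/OR for New CSCR and no effect estimate for Any CSCR.

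**The concern.** Three patients, all free of fellow-eye CSCR at baseline, show how the rule works:

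1. CSCR seen at 3 months, then withdraws: YES.
2. Never CSCR, misses only the 6-month visit, negative at 12 months: MISSING.
3. Never CSCR, withdraws after 9 months: MISSING.

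Whether a patient with a gap has a usable value depends on whether an event was seen. A percentage over YES plus NO then loses only event-free patients.

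Section 5.3.2 keeps patients 2 and 3 as censored observations. The n (%) and the HR/TR/OR on the same line of Table T17 would therefore rest on different patients. Gaps are expected: section 3 allows up to 15% dropout, and section 3.3 tabulates missed visits before study exit as a separate deviation.

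**Working it through.** **Wording.** In section 4.3 the rules for deviations 4 and 8 are limited to visits attended; for deviation 8 the NO rule includes "if CSCR resolved = NO at all attended study visits". Item 14 has no such limit. Taken strictly, it also requires a negative at 1 week, when no fellow-eye assessment is scheduled. A programmer has to guess which visits count.

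**Inputs.** The SAP gives no rate for fellow-eye CSCR, so there is no figure of its own to reproduce here. From the SAP: dropout d = 15% (section 3, an upper limit) and five assessment visits. Assumed: true 12-month risk p in patients free at baseline, equal risk per interval, dropout equally likely after 0, 1, 2, 3 or 4 assessed visits and unrelated to outcome, and share b with fellow-eye CSCR at baseline.

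**Dropout alone, b = 0, p = 10%.**

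- Events seen before dropout: (0.15/5) × Σ(1 − 0.9^(j/5)), j = 0 to 4, = 0.03 × 0.2042 = 0.0061.
- YES: 0.85 × 0.10 + 0.0061 = 0.0911.
- NO: 0.85 × 0.90 = 0.7650.
- MISSING: 1 − 0.0911 − 0.7650 = 0.1439.
- Reported with MISSING excluded: 0.0911/0.8561 = **10.6%** against a true 10%.

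At p = 5% and 20% the same steps give 5.3% and 21.2%. The relative inflation is about 6 to 7%. For 104 patients at p = 10%, that is about 9.5 YES, 79.6 NO and 15.0 MISSING.

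**Adding patients affected at baseline, b = 20%, p = 10%.** They are NO for New CSCR and YES for Any CSCR whatever visits they miss. The denominator is 0.8 × 0.8561 + 0.2 = 0.8849.

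- New: 0.8 × 0.0911/0.8849 = **8.2%**. This is above the true share of all patients (0.8 × 0.10 = 8.0%) but below the at-risk incidence (10%).
- Any: (0.2 + 0.0729)/0.8849 = **30.8%**, against a true 28.0%.

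**Direction in general.** Let m be the share of event-free, baseline-free patients with any gap, and suppose that all events are seen. Then reported New = (1−b)p / [(1−b)p + (1−b)(1−p)(1−m) + b]. This always exceeds (1−b)p when m > 0. It exceeds p only if b/(1−b) < (1−p)m. At p = 10% and m = 15% the right side is 0.135, so the break-even is b = 0.135/1.135 = 11.9%. With b = 0 the reported value is 0.10/0.865 = 11.6%. With b = 20% it is 0.08/0.892 = 9.0%.

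**Missed interim visits.** In a simulation with p = 10%, b = 0, 15% dropout and independently missed visits, the reported value was 13.1% with 5% of visits missed and 16.3% with 10% missed; 32% and 46% of patients were MISSING. These missed-visit rates are assumptions.

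**Simple recoding.** Counting every event-free patient as NO up to the last visit gives 0.0911, or **9.1%**. Leaving out the 3% with no assessment gives 0.0911/0.97 = 9.4%. Both are too low. A Kaplan-Meier estimate returns 10.0% if dropout is unrelated to outcome.

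**The case against.** The strongest reply is that the treatment comparison does not use this coding. Sections 5.3.1 and 5.3.2 and Table T17 make the effect an HR/TR/OR from a model that censors event-free patients. That stands. A reader might infer from item 14, which speaks of comparing the proportion, that an arm with more missed visits would show a spurious treatment effect. The analysis section does not support this; only the descriptive n (%) is exposed.

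Second, the SAP does not say that MISSING leaves the denominator. Section 5.3.8 only has missing data footnoted, and its complete-case rule is for outcomes measured once. This also stands, so the inflation is conditional. The count of YES patients is not inflated in any case.

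Third, the 1-week visit makes the strict reading unworkable, so the author probably meant visits with an assessment. The contrast with deviations 4 and 8 is not decisive either, since deviation 5 refers to all visits without limiting them to those attended. This is a fair account of the likely intent. But removing the 1-week visit still leaves open whether a missed 6-month visit makes the patient MISSING.

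Fourth, MISSING is defensible for a patient who leaves before 12 months, whose 12-month status is unknown. That is true, but a patient with an event before leaving is kept, so the asymmetry remains.

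**Conclusion.** The asymmetry is in the text, and the rule needs correcting. If MISSING is excluded, the reported percentages for Any CSCR, and for New CSCR as a share of all patients, are too high. From the plan's dropout figure alone the excess is modest: about 10.6% for a true 10% with no fellow-eye disease at baseline.

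Two stronger readings are not supported. One is that the New CSCR proportion is always too high. As an at-risk incidence it can be too low, because patients affected at baseline stay in the denominator as NO. The other is that the inflation is known to be large. The 13.1% and 16.3% results rest on missed-visit rates that the SAP does not give.

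All figures also assume a constant risk and dropout unrelated to outcome. The point is minor: it concerns a descriptive figure for a secondary outcome, and neither the primary analysis nor the planned HR/TR/OR is driven by it.

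**What to change.** In section 4.2, item 14:

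- For both variables, define NO over all visits at which the fellow eye was assessed, in place of all post-randomisation visits.
- Use MISSING only when there is no post-randomisation fellow-eye assessment and, for Any CSCR, baseline is not YES.
- Keep the requirement that the fellow eye is free of CSCR at baseline for New CSCR = YES. Without it, pre-existing disease would count as new.
- Restrict New CSCR, both the proportion and the time-to-event model, to patients free of fellow-eye CSCR at baseline, and state this risk set in section 5.3.2.
- In Table T17, report the 12-month proportion with New CSCR as a censored cumulative incidence (Kaplan-Meier or interval-censored) using the section 5.3.2 censoring, with the raw count and its denominator beside it. Recoding to NO and quoting a raw percentage would not be enough.

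The cost is a few lines of text, an amendment and re-approval under section 1.2, and one extra estimate from data already planned. No new data are needed.

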#### 15. Disease recurrence

Disease recurrence will be defined as the appearance of new SRF in a study eye after complete resolution of SRF at any point. The proportion of participants with disease recurrence will be described and time to disease recurrence will be compared between groups.

New variable	Rules
Disease recurrence (study eye)	YES: if complete resolution of SRF in study eye at any study visit = YES AND new SRF in study eye at any study visit after complete resolution = YES
	NO: if Complete resolution of SRF in study eye at any study visit = YES AND new SRF in study eye at any point after complete resolution = NO
	N/A: if complete resolution of SRF in study eye at all study visits = NO
	MISSING: otherwise

Time to disease recurrence

= (date of disease recurrence – date of disease resolution)

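### Patients with fellow-eye CSCR at baseline are counted as non-events for new fellow-eye CSCR, and the censoring rule treats the same patients differently

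*SAP*

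**What the plan says.** Section 4.2, outcome 14, derives three variables.

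- **CSCR in fellow eye at baseline** is YES "if right eye considered for eligibility = YES AND left eye considered for eligibility = YES" and NO "if either right eye considered for eligibility = NO or left eye considered for eligibility = NO". The introduction to the same outcome says that fellow-eye CSCR "will be diagnosed by OCT, FFA, ICGA or AF at baseline, 4 weeks, 3, 6, 9 and 12 months".
- **Any CSCR (fellow eye)** combines baseline disease with disease at any later visit and is only described.
- **New CSCR (fellow eye)** is YES only when baseline status is NO and new CSCR is recorded at a visit after randomisation. It is NO "if either new CSCR in fellow eye = NO at all post- randomisation study visits OR CSCR in fellow eye at baseline" equals YES. The only other category is MISSING.

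The introduction adds that "the proportion with new CSCR in the fellow eye will be compared between groups". Section 5.3.2 lists the outcome under time-to-event data. Its censoring entry reads "Date of last visit, if CSCR not present in fellow eye at any point by the end of follow-up". Table T17 has rows for Any CSCR and New CSCR, with an HR, TR or OR for the latter.

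The analysis population (section 3.5) is all randomised patients less two exclusions, neither of which concerns the fellow eye.

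Outcome 15, disease recurrence, handles a parallel situation differently. It has an N/A category, used "if complete resolution of SRF in study eye at all study visits = NO".

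**The concern.** An incidence needs a denominator of patients who could have the event. A fellow eye that already has CSCR cannot newly acquire it, and the YES rule recognises this by requiring a disease-free baseline. The NO rule then returns the same patients to the denominator as if they had been at risk and escaped. Nothing in sections 3.5 or 5.3.2, or in Table T17, takes them out again.

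The survival analysis has a related gap. Under section 4.2 these patients are non-events. Under section 5.3.2 they do not qualify for censoring, because their fellow eye did have CSCR at some point. One programmer could drop them and another could censor them at the last visit, each with some support in the text.

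At stake are the reported incidence in each arm, the absolute difference between arms and, under one of the two readings, the relative effect.

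**Working it through.** **Inputs.** The planned sample size is 104 (section 3), randomised 1:1 (section 3.2), so 52 per arm. The SAP gives neither the prevalence of fellow-eye CSCR at baseline (q) nor the 12-month incidence among eyes at risk (p). Both are assumed below and varied. The SAP states no figure for this outcome that could be reproduced.

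**1. How the rules treat a patient with fellow-eye CSCR at baseline**

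| Rule | Result |
|---|---|
| New CSCR = YES (4.2, outcome 14) | impossible, needs baseline = NO |
| New CSCR = NO (4.2, outcome 14) | applies |
| Censored at last visit (5.3.2) | does not apply, CSCR was present |
| Parallel case in outcome 15 | N/A |

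**2. Incidence.** Events arise only in the fraction 1 − q, so the proportion under the plan is p × (1 − q). With 10 new cases among 104:

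- Plan: 10/104 = 9.6%.
- q = 20%: 10/(104 × 0.8) = 10/83.2 = 12.0%.
- q = 30%: 10/(104 × 0.7) = 10/72.8 = 13.7%.
- q = 40%: 10/(104 × 0.6) = 10/62.4 = 16.0%.

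**3. Treatment effect, q equal in both arms.** Assume p = 20% on placebo and 10% on eplerenone, so the true risk difference is −10 points, the risk ratio 0.50 and the hazard ratio ln(0.90)/ln(0.80) = 0.472. If the baseline-positive patients are kept as non-events:

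| q | Placebo | Eplerenone | Risk difference | Risk ratio | Hazard ratio |
|---|---|---|---|---|---|
| 10% | 18% | 9% | −9 points | 0.50 | 0.475 |
| 30% | 14% | 7% | −7 points | 0.50 | 0.481 |
| 50% | 10% | 5% | −5 points | 0.50 | 0.487 |

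The absolute difference shrinks by the factor 1 − q. The relative effect hardly changes.

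**4. Treatment effect, q different between arms, no true effect.** The apparent eplerenone:placebo risk ratio is (1 − q on eplerenone)/(1 − q on placebo).

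- Placebo 25%, eplerenone 35%: 0.65/0.75 = 0.87. With p = 15% the proportions are 11.25% and 9.75%, and the hazard ratio is ln(0.9025)/ln(0.8875) = 0.86.
- Placebo 35%, eplerenone 25%: 0.75/0.65 = 1.15. With p = 15% the hazard ratio is 1.16.
- Placebo 40%, eplerenone 20%: 0.8/0.6 = 1.33.

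For the hazard ratio, this bias arises only if the baseline-positive patients enter the model. If the censoring row is read as leaving them out, the model already holds only eyes at risk, and steps 3 and 4 apply to the proportions alone.

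**The case against.** The strongest reply is that the formal comparison is a survival model. If baseline-positive patients are neither events nor censored, they contribute no follow-up time and the model has the right risk set. This stands as one reading, but the NO coding supports the other and the SAP does not choose. What the text shows is an inconsistency, not a survival analysis that is certainly wrong.

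A reader might infer that the hazard ratio will be distorted, since section 5.3.7 reports baseline imbalances. That section does not name the imbalanced factors, so nothing shows that fellow-eye disease is one of them. It also plans a post-hoc adjusted analysis of time-to-event outcomes, which would partly help if it were. The ratios in step 4 rest on assumed splits between arms.

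A reader might also infer that diseased fellow eyes are being called healthy at baseline and later counted as new cases. The SAP does not define the field recording whether an eye was considered for eligibility. It may mean that CSCR was found and the eye therefore assessed, and section 3 defines the study condition by OCT, FFA and ICGA. The YES rule also needs a visit record of new CSCR, which limits old disease being counted. Misclassification is possible but not shown, and I put no figure on it.

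Finally, Table T17 shows Any CSCR beside New CSCR. Their difference is roughly the baseline-positive count, so a careful reader could rebuild the denominator. That mitigates the problem, but the printed percentage would still be on the wrong base and the model's risk set would still be undefined.

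**Conclusion.** The point holds for the denominator and for the conflict between sections 4.2 and 5.3.2. As written, the incidence of new fellow-eye CSCR is understated by the factor 1 − q, and so is the risk difference when q is the same in both arms. With 10 cases among 104 that means 9.6% in place of 12.0% to 16.0% for assumed prevalences of 20% to 40%. The relative effect is nearly unaffected if baseline fellow-eye disease is balanced. It is biased only if baseline-positive patients are kept as non-events and their share differs by arm, which is plausible at 52 per arm but not shown in the SAP.

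The source of baseline status is a secondary point: the eligibility flag is a proxy of unknown meaning in a section that says diagnosis is by imaging, so it needs confirming. This is one of 15 secondary outcomes. The SAP's list linking objectives to outcomes ties it to none of the secondary objectives, and the primary outcome is untouched. It should be corrected before analysis because the correction is simple.

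**What to change.** 1. In outcome 14, code New CSCR as N/A when fellow-eye CSCR is present at baseline, as outcome 15 does for patients who cannot recur.
2. Restrict both the proportion and the time-to-event model to patients whose fellow eye was free of CSCR at baseline, and show that number by arm in Table T17. The subset is defined before randomisation, so the comparison within it remains randomised.
3. Change the censoring row in section 5.3.2 to the date of last visit if there was no new CSCR in the fellow eye.
4. State what the eligibility flag records and confirm that it means CSCR was present. Where baseline fellow-eye imaging findings are already recorded, use them instead.

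Items 1 to 3 change only wording and programming. Their price is a somewhat smaller denominator, for example 72.8 in place of 104 at an assumed 30% prevalence, but the patients removed could not have had the event. Item 4 may cost more if it calls for new grading: the graded imaging variables named in the SAP carry a study-eye prefix, and section 4.3 allows patients with a dye allergy to go without FFA or ICGA. New grading of fellow-eye images is therefore not requested here.
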